Moderate intensity respiratory muscle training (RMT) in ALS

NCT04224961

1. Protocol Title:

Moderate intensity respiratory muscle training (RMT) in ALS

2. Purpose of the Study:

The purpose of this study is to develop treatments that enhance or preserve respiratory strength and provide meaningful clinical improvements for people with ALS and other neurodegenerative diseases with respiratory muscle involvement. Our central hypothesis is that moderate intensity RMT, individually modulated based on RPE, is necessary to induce meaningful changes in respiratory muscle strength and other outcomes in subjects with ALS. Our objectives are to:

- 1) Determine the safety and feasibility of moderate intensity RMT in subjects with ALS targeting both the inspiratory and expiratory muscles using patient-reported ratings of perceived effort (RPE) to monitor and regulate intensity.
- 2) Make preliminary estimates of the effects of moderate intensity RMT on respiratory muscle strength, cough and swallowing, and quality of life.

We expect that moderate intensity RMT regulated with RPE (Foster et al., 2017) will be safe and well-tolerated across subjects, though the magnitude of response, based on changes in respiratory muscle strength, is expected to vary based on baseline respiratory muscle strength. That is, based on effect size calculations, we expect subjects with normal inspiratory muscle strength to demonstrate large to very large increases in respiratory muscle strength, while subjects with mild to moderate inspiratory muscle weakness (40-70% of predicted) will demonstrate a more modest response. Culmination of these objectives will provide pilot data for submission of a competitive NIH grant application to further study RMT in ALS in a larger group of subjects.

3. Background & Significance:

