We will evaluate the feasibility of telehealth visits by conducting assessment of MIP/MEP, device calibration, and RMT via web-based video conferencing. Participants will perform inspiratory and expiratory repetitions at a calibrated, individualized pressure-threshold resistance based on measurement of MIP (for inspiratory training) and MEP (for expiratory training). A licensed speech-pathologist with expertise in RMT (the “RMT clinician”) will provide the intervention following a pre-determined algorithm and shape participant performance with instructions, cues, and demonstrations as necessary to facilitate success during each study visit. Every three weeks, a new RMT cycle will begin and the pressure-threshold target will be adjusted during the web-based visit based on each participant’s current MIP/MEP. Participants and/or caregivers will receive guidance to calibrate the RMT devices to the target pressure-threshold. Calibration will be accomplished by establishing a 3-way connection to a portable differential atmospheric pressure gauge/meter to ensure accuracy of dose delivered (Jones et al., 2016). Intensity of RMT will be monitored and regulated visit based on RPE.

During the initial RMT session (M7), all participants will initiate RMT at 50% of their MIP (for IMT) and MEP (for EMT). The pressure-threshold target will be systematically increased or decreased in 5% increments until moderate intensity is established. Safe, well-tolerated moderate intensity RMT is defined as:

1. RPE between 4-5 and <6 (Foster et al., 1998; see **Figure 3**)
2. Pain rating <4 on a standard 0-10 scale
3. Accuracy $\geq 90\%$ for the last 10 of 25 repetitions in a set
4. Behavioral observations indicate repetitions are well tolerated.

Rating	Descriptor
0	Rest
1	Very, Very Easy
2	Easy
3	Moderate
4	Somewhat Hard
5	Hard
6	-
7	Very Hard
8	-
9	-
10	Maximal

Figure 3. Rating of Perceived Exertion (RPE) Scale.
From Foster C (1998). Monitoring training in athletes with reference to overtraining syndrome. *Med Sci Sports Exerc*, 30, 1164-1168.

Once the appropriate target pressure-threshold is established, participants will then complete 1 set each of 25 repetitions of IMT and EMT at this pressure-threshold to ensure safety and tolerance. Intensity will be adjusted as needed during the session based on the accuracy of repetitions, pain ratings, and behavioral observations to ensure that RMT is moderate in intensity and safe and well-tolerated (see **Figure 4**).

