Instructions for the home-based RMT program will be provided at the conclusion of each RMT therapy session. Participants will gradually increase RMT intensity during each 3-week cycle by increasing the number of repetitions performed. During the first week of each interval, participants will complete 1 set of 25 repetitions for each IMT and EMT 5 days per week (125 IMT and 125 EMT repetitions, cumulatively). During week 2, the number of RMT repetitions will increase to 2 sets of 25 for both IMT and EMT 5 days per week (250 IMT and 250 EMT repetitions, cumulatively). During week 3, 3 sets of 25 repetitions for both IMT and EMT will be completed 5 days per week (375 IMT and 375 EMT repetitions, cumulatively). Overall, participants will be prescribed 6000 RMT repetitions (3000 IMT and 3000 EMT) over the 12-week treatment phase of the study.

Moderate intensity respiratory muscle training (RMT) in ALS

NCT04224961

In weeks 2 and 3 of each 3-week cycle, MIP and MEP will be measured and the RMT Clinician will observe the participant completing the appropriate number of repetitions for the week to ensure safety and tolerance. If the participant reports pain >3 , RPE >5 , accuracy is $<90\%$ for the last 10 of 25 repetitions in a set, or if behavioral observations indicate RMT is poorly tolerated after increasing the number of repetitions, the pressure-threshold target will be systematically decreased in 5% increments until moderate intensity is re-established (see **Figure 5**).

At the beginning of each of the remaining 3-week cycles (M10, M13, M16), the pressure-threshold target will be adjusted in a stepwise fashion with the goal of providing safe, progressive moderate intensity RMT as measured by RPE. The pressure-threshold target will be systematically increased or decreased in 5% increments as previously described until moderate intensity is established.

The maximum training load will be 70% of MIP/MEP, whereas the minimum training load will be 30% of MIP/MEP. This is considered to be the minimum treatment intensity required to induce muscle hypertrophy and strength increases. If a participant is unable to complete RMT repetitions successfully ($\geq 90\%$ accuracy for the last 10 of 25 repetitions in a set) and safely (RPE <6 , pain <4) at 30% MIP/MEP, they will be withdrawn from the research by the PI.

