Participants will be asked to keep a paper log documenting the number of repetitions they complete each day as well as RPE and any pain they experience associated with home RMT.

See **Figure 4** and **Figure 5** for a detailed treatment decision tree and sequential list of treatment activities for each study visit.

10. Risk/Benefit Assessment:

Research participation is expected to be safe and well-tolerated based on our prior research using moderate intensity RMT in late-onset Pompe disease (Jones et al, 2011, 2014, 2016) and the relevant research in the ALS literature (Cheah et al., 2009; Pinto et al., 2012; Plowman et al., 2016). Multiple elements of our study design have been included to ensure rigorous safety monitoring and minimize risk including:

- Individualized, stepwise pressure-threshold resistance based on each subject's respiratory muscle strength and RPE;
- Weekly contact with the RMT clinician during the 12-week training period to foster adherence and assess for any negative side effects;
- A predetermined algorithm for modulating RMT intensity to ensure participant safety;
- Use of an experienced RMT clinician to conduct the RMT program with training and oversight by the PI;
- Calibration of RMT devices to ensure precise and accurate pressure-threshold resistance.

11. Costs to the Subject:

There are no costs to subjects to participate in this study.

12. Data Analysis & Statistical Considerations:

Descriptive statistics will be provided for all outcomes. Primary outcome measures of MIP and MEP will be analyzed using visual analysis of raw data in graphical format using the method described by Land and Gast (2014). Magnitude of change for our primary outcome measures will be determined using

Moderate intensity respiratory muscle training (RMT) in ALS

NCT04224961

Cohen's measure of effect size (d) as defined by the first equation for single-subject d provided by Busk and Serlin (1992). Simply stated, d is obtained by subtracting the mean of the first assessment from the mean of the second assessment, divided by the standard deviation of the first assessment. Effect size calculations will be determined to compare results from baseline (M0-M5) to withdrawal (M19-M24) and pretest (M7) to posttest (M18). We will use conservative interpretation guidelines for effect size calculations in which $d < 0.6$ is negligible, $d \geq 0.6$ modest, $d \geq 1.0$ large, and $d \geq 2.0$ very large.

13. Data & Safety Monitoring:

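### Read literally, the Section 12 effect-size scale gives any fall in MIP or MEP, however large, the same label as stable strength

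*Combined protocol and SAP*

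**What the plan says.** Section 12 (Data Analysis & Statistical Considerations) gives the two primary outcomes, MIP and MEP, two treatments. The first is "visual analysis of raw data in graphical format", by a cited method. The second is a single-subject effect size, introduced with "Magnitude of change for our primary outcome measures will be determined using" and defined in words: "d is obtained by subtracting the mean of the first assessment from the mean of the second assessment", with the SD of the first assessment as divisor. It is applied to baseline versus withdrawal and to pretest versus posttest.

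The interpretation rule follows: "We will use conservative interpretation guidelines for effect size calculations in which $d < 0.6$ is negligible". Modest starts at 0.6, large at 1.0 and very large at 2.0. The section mentions neither an absolute value nor negative d, and it has no class for decline. Descriptive statistics are promised for all outcomes.

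Section 2 gives the purpose as to "develop treatments that enhance or preserve respiratory strength". Section 3 describes respiratory weakness in ALS as progressive.

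**The concern.** Higher MIP and MEP mean stronger muscles, so a loss makes d negative. The lowest class has no lower bound and therefore takes in every negative value. A participant who held steady and one who lost much of their strength would carry the same word, while a gain equal in size to that loss would be called large or very large.

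With maintenance of strength among the aims, a steady participant may be a success and a declining one is not. Negative values are also foreseeable: the baseline-to-withdrawal comparison spans nearly all of the 24 weeks and ends after six weeks without training. A summary by label would separate degrees of gain and merge stability with every degree of loss. Section 3 says the results will help to refine the regimen and to write the analysis plan of a larger study, so the scale could be carried forward.

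**Working it through.** **1. The rule applied to its own formula.** With m1 and m2 the first and second means and s1 the first SD, d = (m2 - m1)/s1. Since s1 > 0, any observed fall gives d < 0, and 0 < 0.6, so the label is negligible whatever the SD. For illustration, take m1 = 60 cmH2O and s1 = 5 cmH2O (both assumed; the documents give neither):

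| Change | d | Label as written | Label with mirrored cut-points |
|---|---|---|---|
| -30% | (42 - 60)/5 = -3.6 | negligible | very large decline |
| -10% | (54 - 60)/5 = -1.2 | negligible | large decline |
| 0 | 0 | negligible | negligible change |
| +10% | (66 - 60)/5 = +1.2 | large | large gain |
| +30% | (78 - 60)/5 = +3.6 | very large | very large gain |

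With an SD of 3 or 10 cmH2O, every fall is still labelled negligible.

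**2. With measurement noise.** Weekly readings were simulated for 200,000 participants per scenario. Strength is stable to week 6, changes linearly over the 12 training weeks and is stable afterwards. Errors are normal and independent. Assumed inputs: a 15% change, and a within-person coefficient of variation (CV) of 6% or 12%. The Section 12 visit labels are read as weeks 0-5 and 19-24, because Figure 1 starts at M1. That gives six readings per side.

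| Result | CV 6% | CV 12% |
|---|---|---|
| 15% loss: median d | -2.7 | -1.3 |
| 15% loss: labelled negligible as written | 100% | 99.9% |
| 15% gain: labelled large or very large as written | 99% | 68% |
| 15% loss: labelled large or very large decline, mirrored | 99% | 68% |

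The second row follows almost automatically from d being negative. The last two rows are the useful ones: mirrored cut-points detect losses exactly as well as the present ones detect gains.

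**3. What mirroring costs in false labels.** For a stable participant with independent readings, m2 - m1 has variance (2/6) x sigma², and s1 has 5 degrees of freedom (df). So d divided by sqrt(2/6) = 0.577 follows a t distribution with 5 df.

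- P(d <= -0.6) = P(t <= -1.04) = 0.173
- P(d <= -1.0) = P(t <= -1.73) = 0.072
- P(d <= -2.0) = P(t <= -3.46) = 0.009

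By symmetry, the present scale already gives a false large or very large gain with probability 0.072. If adjacent readings correlate at 0.5, simulation gives 0.192 in each direction. If all 12 participants were stable, the expected number of false large or very large declines per measure is 12 x 0.072 = 0.9, or 12 x 0.192 = 2.3 with that correlation.

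**4. What d cannot tell.** If strength falls at a steady 10% per 12 weeks through all 24 weeks, with no training effect at all, the median baseline-to-withdrawal d is -2.7 at CV 6% and -1.4 at CV 12%. A decline label describes the change and does not give its cause.

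**The case against.** The best defence is that the classes were meant to grade size only. Section 12 speaks of magnitude, and Section 2 pairs the same size words with a separate word for direction when it predicts how much strength participants will gain. On that reading d = -3 would be reported as a very large decrease. This is plausible as intent, but the rule compares signed d with 0.6 and says nothing of absolute values. Using the absolute value without naming direction would call a severe loss very large and leave the reader to find out which way it went.

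The second defence largely stands. Each of 12 participants is to be graphed with up to 25 weekly readings, descriptive statistics are reported, and the numeric d keeps its sign. No test, success criterion or stopping rule uses the label. The cited visual-analysis method may also classify a falling level or trend; the documents do not reproduce it, so this cannot be settled. A fall would be seen, and only its prescribed name is wrong.

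A reader might go further and infer a gap in safety monitoring. Objective 1 is to "Determine the safety and feasibility of moderate intensity RMT in subjects with ALS", while Section 9 ("Safe, well-tolerated moderate intensity RMT is defined as") lists perceived exertion, pain, accuracy and observed tolerance but not change in strength. The same holds for the rule under which participants who fail at the minimum load are removed ("they will be withdrawn from the research by the PI"). The documents do not support that inference. The Section 9 definition sets the training load in a session and is not the study's safety endpoint. Section 13 has safety and adverse event information collected separately each week of training, and the load is reset to current MIP and MEP every three weeks. Load arithmetic also cannot show that someone losing strength would still meet the exertion, pain and accuracy criteria. Nor would counts of baseline-to-withdrawal declines make a safety result, because they mix in detraining and disease progression.

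**Conclusion.** The point holds as a defect in the labelling rule. The merging of loss with stability follows from the formula and the cut-points and needs no assumption. The sizes in the simulation rest on an assumed loss, assumed CVs and the reading of the visit labels as study weeks.

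The consequence is limited, because other planned outputs show a fall and nothing is decided by the label. It is still worth correcting: the plan prescribes a word that can contradict its own graph, on a primary outcome, in a study for which stability and loss are different answers.

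The false-label rates of about 7% and 19% apply only to baseline versus withdrawal. Pretest versus posttest compares single visits, and the documents do not say which readings supply the SD there. The rate could be higher: with 3 to 5 trials per visit, a within-session CV of 3-8% and a between-session CV of 3-12% (all assumed), simulation gives about 15% to 44% in each direction. It should be treated as not established.

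**What to change.** In Section 12, apply the existing cut-points on both sides of zero and name the direction:

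- -0.6 < d < 0.6: negligible change
- d >= 0.6, 1.0, 2.0: modest, large, very large gain
- d <= -0.6, -1.0, -2.0: modest, large, very large decline

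Report the classes for MIP and MEP under objective 2, for both planned comparisons. Add that d cannot separate the effect of training, detraining and ALS progression, and that it should be read beside the participant's trend in the six-week A1 period.

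The cost is a sentence or two and one reporting line, with no new visit, measurement or threshold. The downside is the noise rate shown above: about 0.9 of 12 stable participants per measure labelled a large or very large decline for baseline versus withdrawal, or about 2.3 if adjacent readings correlate at 0.5. The report should state this, and that it equals the false-gain rate of the present scale.
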